10.1. Training of Investigator and Site Personnel

The training of the Investigator, and appropriate clinical site personnel will be the responsibility of the Study Coordinator and PI, or designee, and may be conducted during an Investigator meeting, a site initiation visit, or other appropriate training sessions. To ensure proper device usage, uniform data collection, and protocol compliance, the Study Coordinator or designee will present a formal training session to study site personnel which will review the Instructions For Use of the device, the Investigational Plan, instructions on data collection, schedules for follow-up with the study site coordinators, and regulatory requirements. Detailed feedback regarding completion of forms will be provided by the Study Coordinator or designee through the regular site monitoring. In order to provide for safe use of the devices the primary concern in operator selection for this study is adequate experience, commitment to safety, and consistency in adherence to the clinical protocol. Therefore, the interventional investigators selected to participate will be neurointerventionalists who, by virtue of their experience and training, are accomplished in cerebral flow restoration techniques using neurothrombectomy devices in intracranial arteries. Each interventional investigator will be experienced, and will have participated in at least 20 for direct aspiration as a first line treatment technique procedures; documentation of experience to be provided before or during site initiation visit.

10.2. Data Monitoring

The Study Coordinator is responsible for ensuring that the study is conducted according to the appropriate regulations. An employee of the Study Coordinator or designate will conduct the following site visits:

10.2.1. Site Qualification

A questionnaire will be sent to each site wishing to participate in order to ensure the investigational site has the appropriate staff, facilities, and expertise to participate in the study.

10.2.2. Site Initiation Visit

Conducted to train the investigational staff on use of the device, study requirements, and other relevant training. The Study Coordinator or a representative will conduct site initiation visits at each investigational site before enrollment begins at that site.

10.2.3. Data Monitoring Site Visit

Conducted as needed to ensure the investigational site is operating in compliance with EN ISO 14155:2011, GCP guidelines, and this protocol, continues to have the appropriate staff and facilities, and is correctly completing the Case Report Forms (CRFs) (verification against source data). To ensure that Investigators and their staff understand and accept their defined responsibilities, the Study Coordinator will maintain regular correspondence and perform periodic site visits during the course of the study to verify the continued acceptability of the facilities, compliance with the investigational plan, and maintenance of complete records. Clinical monitoring will include review and resolution of missing or inconsistent data and source document checks to ensure the accuracy of the reported data. CRFs for all enrolled patients will be made available to the Study

Coordinator for review and collection as agreed with the Investigator. The Study Coordinator will evaluate and summarize the results of each site visit in written reports, identifying repeated data problems with any Investigator and specifying recommendations for resolution of noted deficiencies. The first monitoring visit will be conducted at each site after inclusion of the first patients at each site in order to ensure that all aspects of the protocol are followed as well as to accurately record results, report adverse events, and keep records.

The next periodic monitoring will be performed remotely by the Study Coordinator or its representatives, depending on the enrollment rate at the site and occurrence of adverse events, deviations or any other relevant topics. At least one on-site monitoring visit will be performed before the close-out visit, even if the site does not enroll as many patients as planned.

10.2.4. Study Close-Out Site Visit

Conducted at the termination of this study to resolve any outstanding data queries, and to ensure that any remaining study materials are returned to the Study Coordinator.

10.3. Investigator Requirements

All Investigators must submit the following documentation to be considered approved Investigators:

- 1) Signed and dated recent curriculum vitae
- 2) Signed Clinical Study Agreement (CSA)
- 3) Complete site qualification process and site initiation

The Study Coordinator will make the final determination of activated Investigators. Investigators must allow the Study Coordinator or its representatives to visit the site to periodically assess the data quality and study integrity. On site, the Study Coordinator or its representatives will review study records in comparison with source documents, discuss the conduct of the study and verify that the facilities remain acceptable. In addition, the study may be evaluated by government inspectors who must be allowed access to CRFs, source documents, and other study files.

The Investigator must notify the Study Coordinator promptly of any inspections scheduled by regulatory authorities, and promptly forward copies of inspection reports to the Study Coordinator.

10.3.1. Ethics and Regulatory Considerations

This study will be carried out according to the study protocol, the Declaration of Helsinki from October 2013, the German Medical Device Act (MPG), whereas the § 23b will apply, and the guidelines of ICH-Verordung as well as the General Data Protection Regulation (EU 2016/679). *Participation in this study is voluntary.* The decision to participate or to decline participation will not affect the patient's treatment in any way.

A participant or his/her legal authorized representative can stop the participant's participation in *this study by withdrawing cons*ent, or decide to discontinue participation if participant is no longer able to participate in the study (owing to adverse events, concomitant disease or administrative reasons). If a participant or his/her legal authorized representative decides to withdraw the participant from the study, it can be done at any time. However, the reason for discontinuation must be recorded in the source documentation and on the eCRF.

The data of the participant who withdraws his/her consent will be discarded unless the patient permits further use. In the latter case , data will be used in the final analysis of the study. During the consent procedure the participant or his/her legal representative have the possibility to agree or decline any further use of the data should consent be withdrawn. Furthermore, should the participant or his/her legal representative change their mind, data removal can be requested at any time, and his /her data will be destroyed and not be integrated in the statistical analysis. However, data removal will no longer be feasible once the data has been completely anonymized.

Also, the investigator can decide on the study termination of the participant in case of AEs which make the continuation not desirable, major protocol deviations, or non-compliance of the participant.

Withdrawing consent will not result in any penalty whatsoever for the participant. Further treatment will be performed according to local practice. In case of a device-related or proceduralrelated adverse event that occurred as a result of participating in this study, the participant will be treated according to local practice.

Prior to enrolling patients into the study, the Investigator will ensure that proper Ethics Committee (EC) approval is obtained. The EC shall approve all study documents as appropriate, including the final protocol, amendments to the protocol, Instruction for use and the Informed Consent Form.

The investigator will promptly report to the EC/RB Board all changes in activity and all unanticipated problems involving risks to human participants or others, and will not make any changes in the research without completing any necessary EC/IRB approval steps, except when necessary to eliminate immediate hazards to human participants.

The investigator must report to the EC/IRB at least yearly on the progress of the investigation, if required. A letter from the EC/IRB should document continuing EC/IRB review. Notification to the EC/IRB by the investigator within 3 months after completion, termination, or discontinuation of the study at the specific site must be documented.

Other investigator responsibilities to the EC/IRB and Study Coordinator include the following:

• During the conduct of the study, submit progress reports to the EC/IRB as required.

- As required, obtain approval from the EC/IRB for protocol amendments and for revisions to the informed consent or participant recruitment advertisements. A copy of the correspondence should be provided to the study monitor.
- Notify the EC/IRB (if required) and Study Coordinator of any protocol deviation to protect the life or physical well-being of a participant in an emergency within 24 hours but in no instance later than 5 days after the emergency occurred.
- Provide EC/IRB with any other information it requests before or during the conduct of the study.
- Maintain a file of study-related information that includes all correspondence with the EC/IRB
- Notify EC/IRB within 3 months after study completion, termination or discontinuation.
- Notify Study Coordinator, within 24 hours, of withdrawal of approval by the reviewing EC/IRB.

Informed Consent

Informed consent has to be obtained prior to enrolment of patients in SESAME. In the normal case written consent will be given by the patient after detailed information about the clinical trial by the investigator. The investigator or sub-investigator will explain the study in detail including risks and benefits for the patient, financing of the study and potential conflicts of interest. Furthermore, the investigator will clarify that the patient or his/her legal guardian will document his/her agreement to participate in the SESAME study by signing the informed consent form.

However, given the sample to be studied (i.e. acute stroke patients showing neurological deficits that may comprise aphasia or disturbance of consciousness) we expect that a certain proportion of patients (estimated 60%) will be unable to give informed consent. Excluding this group of patients from the clinical trial would entail severe scientific and clinical drawbacks. Results would be biased by systematically excluding more severe strokes and patients with aphasia, i.e. mostly left hemispheric strokes. As a consequence, the generalizability of the study results would be limited. Strictly speaking, in case of a positive result this could not be transferred to the patients excluded from the trial (e.g. aphasic patients). This large group would still be excluded from this effective treatment.

A possible solution would allow the *enrolment of patients unable to give informed consent* based on their alleged will following pre-specified criteria. These criteria would have to consider a potential individual benefit as well as any possible risk of participation in the clinical trial. In general the protection of the patient and his autonomy has to be weighed against the potential individual benefit as well as the scientific interest. Following European and national regulations the enrolment of patients (temporarily) unable to give informed consent into clinical trials is possible in an emergency situation if a legal guardian is available and – after careful consideration of possible risks and potential individual benefit – a participation in the clinical trial would comply with the patient's presumptive will. Moreover, standard treatment following best medical practice must not be withheld to the patient by enrolment in the clinical trial.

For patients eligible for enrolment in SESAME best medical practice in these patients usually comprises the use of CT to rule out hemorrhage or prove ischemic infarction followed by an interventional procedure (thrombectomy), hospitalization and monitoring in a specialized stroke unit. Additional standard treatment consists of supervision and modification of physiological parameters (such as blood pressure, body temperature, blood glucose) and early secondary prevention (e.g. Aspirin).

Suggestion for enrolment of patients unable to give informed consent in SESAME:

[figure not shown]
- A Patient is able to give informed consent and able to provide written consent:
 - Patient is informed by investigator, patient information is handed over to the patient, and patient provides written consent. This may occur prior to treatment or after treatment if the patient was unable to give informed consent and underwent standard of care treatment in agreement with the protocol.
- B Patient is unable to give informed consent, legal guardian is available

Legal guardian acts on behalf of the patient; legal guardian is informed by investigator, patient information is handed over to the legal guardian, legal guardian provides written consent

C –Patient is unable to give informed consent; legal guardian is not available, enrolment of patient by consensus between investigator and independent physician

If the patient is unable to give informed consent and no legal guardian has been appointed, the patient may be enrolled by consensus between the investigator and an independent physician about an the presumed will of the patient; if possible, patient's next of kin should be contacted to appraise the patient's presumed will; the decision has to be documented using a special form. Immediately parallel an application for appointing a legal guardian will be started later patient or legal guardian will be informed by the investigator and may or may not provide written consent. Enrolment through the independent physician will be included to minimize selection bias.

Figure 1: "Overview of Ways of Obtaining Informed Consent"

These options for obtaining the informed consent are NOT equal or interchangeable. The highest priority will always be to obtain informed consent by the participant himself. Only if this option is not possible, other ways may be approached.

Data collection will not start prior to informed consent but may be done retrospectively. All information and data are subject to medical professional confidentiality, including patient's names, other confidential data as well as sensitive medical information. Data sent to Study Coordinator or Core Labe concerning participants or their participation in this study will be considered confidential. All information and data captured in EDC system or sent to Study Coordinator will be deidentified information. All data used in the analysis and reporting of this evaluation will be used in a manner without identifiable reference to the participant. The Principal Investigator consents to visits by the staff of the Sponsor and its authorized representatives as well as regulatory authorities, which governs the conduct of clinical investigations.

Data will be fully anonymized as soon as legally and practically (for study purposes) possible.

Study Financing and Conflicts of Interest

Financial support for the SESAME study will be pro MicroVention Europe, a French limited liability company, with capital of 40 000€, registered with the Registry of Commerce and Companies in

Versailles under number 440 775 674 RCS, with registered address at [name], [name], France.

The financing of the study will provide case fees to reimburse investigators and study nurses for data collection at the study sites as well as central administrative costs such as project management, study monitoring, data managment, CEC meetings etc.. Study participants will not be reimbursed or receive any other incentives for study participation. Similarly, investigators will not receive any incentives for enrolling participants into the study.

MicroVention Europe will have no access to the study participant data and will not be involved in patient recruitment, study design or analysis and interpretation of the data. However, the Study Coordinator will provide regular updates about the study progress including fully anonymized patient statistics to MicroVention Europe.

Publication of study results will disclose financial support.

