	tients suffering an Acute Ischemic Stroke when assessed at 24 hours, dis-			
	charge and 90 days after treatment.			
Sample Size & Duration	250 patients will be enrolled. All patients will be followed for 90 days or			
of Study:	until death.			
Number of Sites:	Up to 20 European sites (France, Germany, Austria, Italy, Netherlands)			
Allocation:	Non-randomised, single arm			
Patient Population:	Patients who are at least 18 years of age presenting with an acute ischem-			
	ic event in the anterior cerebral circulation that can be treated within 6			
	hours from AIS symptom onset. Those eligible to be treated with SOFIA™/			
	SOFIA™ PLUS will be enrolled after having signed an informed consent			
	form (or having one signed on his or her behalf by a legally authorized			

	representative or an independent physician).				
Patient Selection Crite- ria: Target Enrollment Peri-	cal and imaging considerations. Patients who meet all of the inclusion criteria and none of the exclusion criteria will be eligible for study partici- pation.				
od & Study Duration:	enrollment of the first patient and end upon enrollment of the last patient into the study. Total study duration is estimated to be up to 45 months (up to 42 months of enrollment + 3 months of follow-up).				
Inclusion Criteria:	 Participant is ≥ 18 Demonstrated occlusion of the distal intracranial carotid artery, middle cerebral artery (M1 or M2) or anterior cerebral artery (A1 or A2) proven by CT and/or MRI 				
	 NIHSS ≥ 2 and ≤ 30 at screening Start of the thrombectomy procedure within 6 hours of the onset of stroke symptoms Pre event mRS ≤1 				
	 5. Pre event firks ≤1 6. Informed consent by the patient, legal guardian, or inclusion of patient under presumptive will after consultation of an independent physician and statement of investigator 				
Exclusion Criteria:	1. Patient is more than 6 hours from symptom onset				
	2. Rapidly improving neurologic examination				
	3. Evidence of cerebral ischemia in the posterior circulation				
	4. Severe unilateral or bilateral carotid artery stenosis requiring stent treat- ment				
	5. Presence of an existing or pre-existing large territory infarction				
	6. Absent femoral pulses				
	7. Excessive vascular tortuosity that will likely result in unstable access				
	8. Pregnancy; if a woman is of child-bearing potential a urine or serum beta HCG test is positive				
	9. Known contrast product allergy				

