5.4. Enrollment

Once all inclusion/exclusion criteria are met, the patient is enrolled when a SOFIA[™]/ SOFIA[™] PLUS Catheter is inserted in the patient and will be assigned a five digit identification number (participant study number). The first two digits assigned represent the site identification, followed by a hyphen and three subsequent digits which represent the sequential enrollment number. For example, ID: 04-002 would represent the second participant enrolled at site 04.

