5.12. Termination of Patient Participation

All patients have the right to terminate their participation at any point during the study. In addition, Principal Investigators also have the ability to terminate patient participation in the study. Reasons for termination include: completion of study, patient withdrawal, physician-directed patient withdrawal, lost-to-follow-up, and death. A description of the reason for their termination will be documented in the patient's medical file and in the appropriate study Case Report Forms (CRF).

Withdrawal:

A participant or his/ her legal authorized representative can stop the participant's participation in this study by withdrawing consent, or decide to discontinue participation if the participant is no longer able to participate in the study (owing, concomitant disease or administrative reasons). If a participant or his/ her legal authorized representative decides to withdraw the participant from the study, it can be done at any time. Whenever possible, the reason for discontinuation should be recorded in the source documentation and on the eCRF. Withdrawing consent will not result in any penalty whatsoever for the participant. Further treatment will be performed according to local practice. The data of the participant who withdraws his/her informed consent, collected prior to withdrawal, will not be discarded, and will be used in the final analysis of the study. Lost to follow-up:

After three documented attempts to reach the participant by telephone have failed, a certified letter will be sent to the participant. The participant will be considered lost to follow-up if this communication is unsuccessful.

Participants who discontinue study participation prematurely will not be replaced.

6 Assessment of Safety and Effectiveness

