9.2.1. Definition of Analysis Samples

All primary and secondary Effectiveness and safety outcome measures will be analyzed under both the intent-to-treat (ITT) and per-protocol (PP) principles.

a) Intent to Treat Sample

The ITT sample includes all participants who are enrolled.

b) Per Protocol Sample

The per-protocol sample will include all participants that do not have the following protocol violations or deviations:

1) Eligibility violation

2) No Sofia/Sofia Plus treatment performed

3) mRS primary effectiveness only: missing 90-day outcome (not including missing due to death prior to the 90 days)

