9.2.2. Effectiveness

Primary Endpoints

The primary effectiveness variable is the Clinical outcome defined as mRS \leq 2 at 90 days (assessment performed by an independent neurologist)

The proportion of patients who are successful based on each criterion will be calculated. Estimates of the group differences and their 95% confidence intervals will be calculated. Multiple ordinal logistic regression analysis estimated the effect of treatment and tested for the interaction of time to reperfusion with treatment. The effect of treatment as a risk difference on reaching independence (mRS score, 0-2) will be computed as a function of time to reperfusion. Whenever appropriate, calculations will be adjusted for age, National Institutes of Health Stroke Scale score, previous stroke, atrial fibrillation, diabetes mellitus, smoking status and intracranial arterial terminus occlusion. For missing data (patients who were lost to follow-up) the mRS scores at 90 days will be assigned using multiple imputations, worst case scenario (mRS = 6), and best case scenario (mRS=0).

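### Investigators may end participation after the one-time procedure, including for adverse events, and nothing keeps 90-day follow-up going, so the per-protocol good-outcome rate can be biased upward

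*Protocol*

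**What the plan says.** Two sections give the investigator the power to end participation. Section 10.3.1 states that "the investigator can decide on the study termination of the participant in case of AEs which make the continuation not desirable", and names major protocol deviations and non-compliance as further grounds. Section 5.12 states without criteria that "Principal Investigators also have the ability to terminate patient participation in the study". Its list of reasons is "completion of study, patient withdrawal, physician-directed patient withdrawal, lost-to-follow-up, and death", so a physician-directed exit is a category separate from loss to follow-up. The same section adds: "Participants who discontinue study participation prematurely will not be replaced".

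The synopsis (Sample Size & Duration of Study) says: "All patients will be followed for 90 days or" until death. Under section 5.4 a patient is enrolled when the "PLUS Catheter is inserted in the patient and will be assigned a five digit identification number". Section 5.10 asks for a Study Completion Form at early exit, but it does not ask for the mRS or adverse events to be collected afterwards.

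On analysis, the synopsis names the per-protocol population for primary and secondary endpoints, while section 9.2.1 plans both intention-to-treat and per-protocol analyses. For the primary mRS endpoint, the per-protocol set in 9.2.1 excludes patients with a "missing 90-day outcome (not including missing due to death prior to the 90 days"). Section 9.2.2 states: "For missing data (patients who were lost to follow-up) the mRS scores at 90 days will be assigned using multiple imputations", together with a worst-case score of 6 and a best-case score of 0.

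**The concern.** The device is used once, at or right after enrolment. Ending participation later spares the patient no study treatment. What remains is a routine mRS assessment, a questionnaire and adverse event reporting, and these are what stop. A patient who wants to leave already has the right to withdraw consent.

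Of the three grounds, adverse events are the one plainly linked to outcome. If patients with a complicated course are the ones whose 90-day mRS goes uncollected, missingness depends on the primary endpoint, and the per-protocol definition then takes them out of the denominator. The imputation rule is worded for patients lost to follow-up, which section 5.12 treats as a different category. At stake is an upward bias in the good-outcome rate, and the loss of later events from the endpoint of device- and procedure-related adverse events within 90 days.

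**Working it through.** **The plan's own figure.** Inputs from section 9.1: expected rate p = 32.6%, half-width d = 6.0 points, two-sided 95% interval, 236 patients, 250 enrolled, 5% lost to follow-up.

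- n = z²p(1−p)/d² = 1.96² × 0.326 × 0.674 / 0.06² = 234.5, so 235 against the stated 236.
- Half-width at 236: 5.98 points.
- At 250 × 0.95 = 237.5 evaluable patients: 5.96 points.

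The sample size reproduces and is not in dispute. Its 5% allowance names only loss to follow-up.

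**Effect on the per-protocol rate.** Let k of N = 250 patients be terminated with a missing mRS, and let q be the good-outcome rate they would have had. The protocol gives neither k nor q; both are assumptions. Expected good outcomes are 250 × 0.326 = 81.5.

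Observed rate = (Np − kq)/(N − k), and shift = k(p − q)/(N − k).

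| Terminated | q | Observed rate | Shift |
|---|---|---|---|
| 12 (about 5%) | 0% | 81.5/238 = 34.2% | +1.6 points |
| 12 (about 5%) | 10% | (81.5 − 1.2)/238 = 33.7% | +1.1 points |
| 25 (10%) | 0% | 81.5/225 = 36.2% | +3.6 points |
| 25 (10%) | 10% | (81.5 − 2.5)/225 = 35.1% | +2.5 points |

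The shift is upward whenever q is below 32.6%. The 10% rows assume twice the whole loss allowed for in section 9.1, all from this one cause.

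**Effect under intention-to-treat.** If section 9.2.2 were applied to the same patients:

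- Worst case (mRS 6): with 12 terminated, 81.5/250 = 32.6% (q = 0) or 80.3/250 = 32.1% (q = 10%). With 25 terminated, 32.6% or 79/250 = 31.6%. The result is unbiased or slightly conservative.
- Best case (mRS 0), q = 0: (81.5 + 12)/250 = 37.4% with 12 terminated, and (81.5 + 25)/250 = 42.6% with 25.

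**Effect on safety.** Of the five safety endpoints in section 9.2.3, four close at the end of the procedure, at 24 hours or at discharge. Only the device- and procedure-related adverse events run to day 90. The event that prompts a termination has already happened, and section 9.2.7 counts patients reporting an event, so that patient is in the numerator. What a termination after discharge can lose is further events in the 90-day endpoint.

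**The case against.** The strongest reply is that the protocol already has safeguards. Section 9.2.1 plans intention-to-treat analysis of all enrolled patients beside the per-protocol one, and section 9.2.2 includes a worst-case score that removes the favourable shift. The reference to loss to follow-up in 9.2.2 could be read as a loose gloss on missing data, and an analysis plan could spell out each reason for missingness. Known deaths before day 90 stay in the per-protocol set. Adverse events are observed from the start of the procedure (6.1), serious ones are reported within 24 hours, and a committee adjudicates them (10.4). The rule is permissive and may rarely be used.

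Most of this stands, and it rules out several stronger readings that a reader might draw:

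- That the rule removes complicated cases as a matter of course. The text only allows it, and gives no frequency.
- That adverse event rates as a whole are biased down, or that a perforation would vanish. Neither section says that data are discarded when the investigator ends participation, and a perforation is recorded at the procedure.
- That all three grounds select patients who do badly. The documents do not show this for major deviations or non-compliance.
- That participation after insertion should end only by completion, death, consent withdrawal or loss to follow-up. That list has no place for a patient enrolled on presumed will who, or whose guardian, later gives no consent. Sections 8.1 and 10.3.1 provide for that case.

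The reply does not dispose of the point. The synopsis names the per-protocol population, and the definition in 9.2.1 drops these patients. The imputation wording does not reach them. A death after termination counts only if someone ascertains it. An analysis plan can extend an imputation rule, but it cannot recover outcomes that sites were allowed not to collect.

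**Conclusion.** The point holds as a design weakness and an internal contradiction. Sections 10.3.1 and 5.12 allow participation to end before day 90 at the investigator's decision, no section keeps follow-up going, and the synopsis says all patients are followed for 90 days or until death. Termination for adverse events can make the primary outcome missing for reasons related to it, with an upward bias in the per-protocol rate.

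The likely size is modest: 1.1 to 1.6 points at about 5% termination, against a planned half-width of 6 points. That rests on an assumed termination rate, on an assumed 0 to 10% good-outcome rate in those patients, and on a complete-case per-protocol analysis as defined in 9.2.1. The loss on safety is limited to later events in the 90-day endpoint. The change is worth making because it is cheap and because missing follow-up cannot be restored at analysis.

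**What to change.** 1. In sections 10.3.1 and 5.12, either remove adverse events, major protocol deviations and non-compliance as grounds for ending data collection, or state that after any investigator-directed termination the 90-day mRS, vital status and adverse events are still collected from routine visits. Make the exception explicit: collection stops if consent is withdrawn or not given, including for patients enrolled on presumed will. This brings both sections into line with the synopsis and leaves clinical care untouched.
2. In section 9.2.2, apply the missing-data rule to a missing 90-day mRS for any reason, not only loss to follow-up.

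The cost is a wording amendment to three sections and a few more 90-day contacts in patients with a difficult course, at visits that are already routine.
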